### 6.5.2. Management of Hyperphosphatemia

Hyperphosphatemia is an expected on-target pharmacologic effect of FGFR inhibition. Hyperphosphatemia should be managed with diet modifications, phosphate binders and diuretics, or a dose reduction per the recommendations in [Table 13](#).

The use of diet modifications alone include food exchanges from high-phosphate foods to low-phosphate foods and can be implemented once serum phosphate levels are above the ULN but do not exceed 7.0 mg/dL. Diet modification should continue with the inclusion of phosphate binders once serum phosphate levels exceed 7.0 mg/dL. Examples of phosphate binders are sevelamer HCl (examples of brand names: Renegel® or Renvela®) or lanthanum HCl.

Administration of phosphate binders should be 3 times per day (eg, with each meal) to reduce absorption of phosphate. Doses and frequency of doses should be based on the participant's tolerance for the binder and the control of serum phosphate. If binders are used to manage hyperphosphatemia during treatment, it is recommended to stop binders at the same time pemigatinib is stopped to reduce the risk of hypophosphatemia.

For grading of hyperphosphatemia, please note that CTCAE v5.0 now has a category for hyperphosphatemia.

For Japanese participants, the phosphate binders bixalomer or lanthanum carbonate hydrate will be provided by the sponsor for the treatment of hyperphosphatemia, when required (see [Table 13](#)).

**Table 13: Recommended Approach for Hyperphosphatemia Management**

Serum Phosphate Level	Supportive Care	Guidance for Interruption/Discontinuation of Pemigatinib	Guidance for Restarting Pemigatinib
> 5.5 mg/dL and ≤ 7 mg/dL	Initiate a low-phosphate diet.	No action.	Not applicable.
> 7 mg/dL and ≤ 10 mg/dL	Initiate/continue a low-phosphate diet and initiate phosphate-binding therapy. Monitor serum phosphate approximately twice a week and adjust the dose of binders as needed; continue to monitor serum phosphate at least twice a week until level returns to ≤ 7 mg/dL.	If serum phosphate level continues to be > 7 mg/dL and ≤ 10 mg/dL with concomitant phosphate-binding therapy for 2 weeks, or if there is recurrence of serum phosphate level in this range, interrupt pemigatinib for up to 2 weeks.	Restart at the same dose when serum phosphate is < 7 mg/dL. If serum phosphate level recurs at > 7 mg/dL, restart pemigatinib with dose reduction.
> 10 mg/dL	Continue to maintain a low-phosphate diet, adjust phosphate-binding therapy, and start/continue phosphaturic agent. Continue to monitor serum phosphate approximately twice a week until level returns to ≤ 7 mg/dL.	If serum phosphate level is > 10 mg/dL for 1 week following phosphate-binding therapy and low-phosphate diet, interrupt pemigatinib. If there is recurrence of serum phosphate level in this range following 2 dose reductions, permanently discontinue pemigatinib.	Restart pemigatinib at reduced dose with phosphate binders when serum phosphate is < 7 mg/dL.

### 6.5.3. Up-Titration

Any participant who does not reach the target serum phosphate level of  $> 5.5$  mg/dL at any time during Cycle 1, are compliant with taking study drug, and do not experience an ongoing Grade 2 or higher treatment-related AEs will increase the daily dose to 18 mg starting from Cycle 2 Day 1.

Participants who are titrated up to 18 mg QD will begin the next cycle at the new dose level and must agree to all Cycle 1 assessments (█ safety assessments [hematology and blood chemistry]). Up-titration may occur no earlier than on Day 1 of Cycle 2, so that participants are observed for phosphate level and AEs at least for 1 cycle.

For participants who are up-titrated from 13.5 mg to 18 mg, dose reductions are allowed (see Section 6.5.1).

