AUC for pemigatinib 18 mg was estimated using a linear exposure relationship. Maximal serum phosphate change from baseline for each individual was then estimated using a population model. The maximal serum phosphate after treatment with pemigatinib 18 mg was calculated by adding the baseline of serum phosphate. The simulation suggested that the serum phosphate would increase above 5.5 mg/dL after treatment with pemigatinib 18 mg for the participants treated with pemigatinib 13.5 mg who did not develop hyperphosphatemia.

**Figure 2: Comparison of Steady-State Exposures for Pemigatinib 13.5 mg QD Between Participants With Nonhyperphosphatemia and Hyperphosphatemia (C1D8)**

AUCss = area under the curve at steady state; HP = hyperphosphatemia.

Any participant who does not reach the target serum phosphate level of > 5.5 mg/dL at any time during Cycle 1, and who is compliant with taking study drug and does not experience an ongoing Grade 2 or higher treatment-related AEs, will increase the daily dose to 18 mg starting at Cycle 2 Day 1.

A CYP3A4-mediated drug-drug interaction study (INCB 54828-104) indicated there is evidence of a clinically significant effect on pemigatinib exposure when coadministered with a potent CYP3A4 inhibitor, itraconazole (increased pemigatinib AUC by 88%) or potent CYP3A4 inducer, rifampin (decreased pemigatinib AUC by 85%). A PBPK model was developed and validated using in vitro and clinical DDI data. PBPK model–simulated pemigatinib AUCs were increased by approximately 50% for moderate CYP3A4 inhibitors and decreased by more than

50% for moderate CYP3A4 inducers. In addition, PBPK modeling shows no DDI effect when pemigatinib was coadministered with a weak CYP3A4 inhibitor or inducer.

Dose modifications for tolerability issues are noted in Section [6.5](#).

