#### **6.5.1. Criteria and Procedures for Dose Interruptions and Adjustments of Study Drug**

Safety concerns should be discussed with the sponsor immediately upon occurrence or awareness to determine if the participant should continue or discontinue study treatment.

Treatment with pemigatinib may be delayed up to 2 weeks (14 days) to allow for resolution of toxicity. Participants may resume treatment if no medical condition or other circumstance exists that, in the opinion of the investigator, would make the participant unsuitable for further participation in the study. The treating investigator should contact the sponsor to discuss the case of any participant whose treatment has been delayed for more than 14 days before restarting treatment with pemigatinib. See [Table 12](#) for guidelines.

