**Table 12: Guidelines for Interruption and Restarting of Study Drug**

Adverse Event	Action Taken
Chemistry	

 
AST and/or ALT is <math>> 5.0 \times</math> ULN.
 
 
Note: In participants with liver metastasis-related elevations at baseline, contact sponsor to discuss clinical management and possible dose reductions.
	
Step 1: Interrupt pemigatinib up to 2 weeks (14 days) until the toxicity has resolved to <math>\leq</math> Grade 1 except by approval of the medical monitor.
 
Step 2: Restart pemigatinib at same dose. If assessed as related to pemigatinib, restart pemigatinib at next lower dose; monitor as clinically indicated.

Other toxicities	

 
Any Grade 1 or Grade 2 toxicity.
 
	
Continue pemigatinib treatment and treat the toxicity; monitor as clinically indicated.

 
Any Grade 3 toxicity, if clinically significant and not manageable by supportive care.
 
	
Step 1: Interrupt pemigatinib up to 2 weeks (14 days), until toxicity resolves to <math>\leq</math> Grade 1.
 
Step 2: Restart pemigatinib at same dose. If assessed as related to pemigatinib, restart pemigatinib at next lower dose; monitor as clinically indicated.

 
Any recurrent Grade 3 toxicity after 2 dose reductions.
 
	
Discontinue pemigatinib administration and follow-up per Protocol. (Exceptions require approval of sponsor.)

 
Any other Grade 4 toxicity.
 
QT/QTc to <math>> 500</math> milliseconds or to <math>> 60</math> milliseconds over baseline.
 
	
Discontinue pemigatinib administration and follow-up per Protocol.

The sponsor recommends a maximum of 2 dose level reductions: participants administered 13.5 mg can decrease to 9 mg, and if additional dose reduction is required, participants can decrease to 4.5 mg. Dose reductions below 4.5 mg are not allowed. The frequency of dosing remains the same (QD) as well as the schedule (continuous dosing). After a dose reduction, a dose re-escalation is not permitted.

For participants who are up-titrated from 13.5 mg to 18 mg, study drug can be decreased to 13.5 mg, and if additional dose reductions are required, participants can decrease to 9 mg and then to 4.5 mg. Dose reductions below 4.5 mg are not allowed.

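### The up-titration rule, read as written, sends some participants already reduced to 9 mg up to 18 mg, against the ban on re-escalation in Section 6.5.1

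*Protocol*

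**What the plan says.** **Up-titration.** Protocol Section 6.5.3 applies to any participant and sets three conditions: serum phosphate never above 5.5 mg/dL during Cycle 1, compliance with study drug, and no ongoing related adverse event of Grade 2 or higher. Those who meet them and "do not experience an ongoing Grade 2 or higher treatment-related AEs will increase the daily dose to 18 mg" do so from Cycle 2 Day 1. Section 2.2.2 repeats the rule: a participant who "does not experience an ongoing Grade 2 or higher treatment-related AEs, will increase the daily dose to 18 mg".

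**Reduction and re-escalation.** Table 12 in Section 6.5.1 covers "Any Grade 3 toxicity, if clinically significant and not manageable by supportive care". Dosing is held until the toxicity is Grade 1 or less, and then: "If assessed as related to pemigatinib, restart pemigatinib at next lower dose; monitor as clinically indicated". From 13.5 mg the next lower dose is 9 mg. On the length of a hold, Section 6.5.1 says: "Treatment with pemigatinib may be delayed up to 2 weeks (14 days) to allow for resolution of toxicity". The paragraph below Table 12 that sets out the 13.5, 9 and 4.5 mg steps ends with "After a dose reduction, a dose re-escalation is not permitted".

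**Links between the two.** Section 6.5.3 refers to 6.5.1 only for what happens after up-titration: "For participants who are up-titrated from 13.5 mg to 18 mg, dose reductions are allowed". Section 6.5.1 has a matching paragraph: "For participants who are up-titrated from 13.5 mg to 18 mg, study drug can be decreased to 13.5 mg".

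**The concern.** The two rules collide for one kind of participant: a compliant person reduced from 13.5 to 9 mg during Cycle 1 for a related adverse event that is no longer Grade 2 or higher, whose phosphate never rose above 5.5 mg/dL. All three up-titration conditions are met, so 6.5.3 and 2.2.2 call for 18 mg. Section 6.5.1 forbids any increase above 9 mg.

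At stake is participant safety. A site working from 6.5.3 alone would give the highest dose in the study to someone who has just needed a reduction at a lower one. A site working from 6.5.1 would not. Section 2.2.2 supports 18 mg with a simulation in participants treated with 13.5 mg who did not develop hyperphosphatemia. It does not address people held and reduced for toxicity.

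A participant who was only interrupted and restarted at 13.5 mg is outside this point. So is one reduced for high phosphate under Table 13, because that participant fails the phosphate condition.

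**Working it through.** The plan gives no figure to reproduce. The check is whether the situation can arise under the protocol's own steps, and what dose change would follow.

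**1. The conditions, taken in turn, for a related Grade 3 event in week 1**

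- *Adverse event.* Table 12 requires Grade 1 or less before the 9 mg restart. The event is then no longer an ongoing Grade 2 or higher event, so it does not block up-titration.
- *Compliance.* Protocol Section 6.4 sets no threshold. The formula in SAP Section 6.5 is 100 × dose taken / dose prescribed, with the prescribed dose accounting for modifications. Taking every 9 mg tablet as prescribed gives 100%. Nothing ties that formula to the condition in 6.5.3, but no text treats a prescribed reduction as non-compliance.
- *Phosphate.* Met if no Cycle 1 value exceeds 5.5 mg/dL.
- *Current dose or earlier reduction.* Not a condition in either section.

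**2. Does the sequence fit in Cycle 1?** Inputs: a 21-day cycle (Section 2.2.2) and a hold of up to 14 days (Section 6.5.1). Let *h* be the first held day and *L* the length of the hold. Restart is on Day *h* + *L*, and a restart within Cycle 1 needs *h* + *L* ≤ 21.

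- *L* = 14: *h* ≤ 7.
- *L* = 7: *h* ≤ 14.

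So even the longest standard hold fits if it starts by Day 7.

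**3. Could the hold itself help meet the phosphate condition?** Table 4 schedules on-treatment chemistry in Cycle 1 at nominal Days 8 and 15. A 14-day hold covers Days *h* to *h* + 13. It spans both days if *h* ≤ 8 and *h* + 13 ≥ 15, that is, *h* = 2 to 8. Combined with *h* ≤ 7 from step 2, this gives *h* = 2 to 7 and a restart on Day 16 to 21. Section 2.2.2 describes the phosphate rise as exposure-dependent, so values taken off drug are less likely to exceed 5.5 mg/dL. The ± 3-day visit windows and unscheduled tests may still catch a rise.

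**4. Size of the dose step**

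| Step | Ratio | Change |
|---|---|---|
| 13.5 to 18 mg (the step the text describes) | 18/13.5 = 1.33 | +33% |
| 9 to 18 mg (6.5.3 applied to a reduced participant) | 18/9 = 2.00 | +100% |

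Under the linear exposure relationship used in Section 2.2.2, the AUC ratios are the same: 2.00 times the AUC at 9 mg, and 1.33 times the AUC at the 13.5 mg dose on which the event occurred.

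**5. Is there a tie-breaker?** Section 6.5 asks for clinical judgment and medical monitor consultation but does not rank the rules. Section 6.5.3 points to 6.5.1 only for later reductions. The SAP does not address up-titration. No precedence rule appears in either document.

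**The case against.** The strongest reply is that the protocol, read as a whole, already settles the case.

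- The ban closes the very paragraph that describes participants going from 13.5 to 9 mg, and a separate paragraph deals with those up-titrated. A flat prohibition aimed at the reduced group could be read as more specific than the general sentence in 6.5.3.
- Every description of up-titration starts from 13.5 mg, including one inside 6.5.3. Nowhere is a step from 9 to 18 mg described.
- The ban is the later clarification: Amendment 3 (Appendix F, item 14) added it, with investigator feedback among the reasons.
- There are safeguards. Table 3 asks sites to assess for up-titration, Section 6.5.1 asks for immediate discussion of safety concerns with the sponsor, and Section 6.5 involves the medical monitor. The IRT Manual and site files, which are not among the documents, may say more.
- The subset is narrow, and Section 6.6.1 calls 20 mg QD tolerable.

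Much of this stands. The ban is probably what the sponsor intends, the safeguards make an error less likely, and the subset is likely small. But a description of the usual starting dose is not an eligibility condition, and none of the listed text says which rule yields. The protocol uses separate terms for up-titration and re-escalation without saying that the ban on one limits the other. Item 14 of Amendment 3 names only Section 6.5.1, and 6.5.3 carries no matching condition. Section 6.5.3 is mandatory in its wording. General tolerability of 20 mg does not show tolerance in someone who needed a reduction at 13.5 mg.

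**Conclusion.** The concern holds. For the participant described, Sections 6.5.3 and 2.2.2 as written require 18 mg and Section 6.5.1 forbids it, with no stated order between them. This is a contradiction between two dosing rules, not merely a missing detail, and one of them is unsafe if followed literally. It should be fixed.

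The dose consequence is a doubling from 9 mg, or 1.33 times the dose on which the event occurred; the exposure ratios rest on the linear relationship in Section 2.2.2. The number of participants affected cannot be derived from the documents. There is no effect on sample size, alpha or power.

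The conclusion rests on the protocol and SAP alone. Instructions in the IRT Manual or site files could reduce the practical risk but would not remove the conflict in the protocol.

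**What to change.** Add one condition to the up-titration rule in both Section 6.5.3 and Section 2.2.2: the participant *is receiving 13.5 mg QD and has had no dose reduction during Cycle 1*. Both sections then agree with the ban in 6.5.1. Check that the IRT dose-assignment rules match; whether they need changing cannot be judged from the documents.

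The cost is one clause in two places, which can go into the next amendment with the IRB/IEC approval that Section 11.1 requires. No new data, procedures or participants are needed. The downside is that a few participants reduced in Cycle 1 will not be up-titrated. Whether a toxicity-related interruption without a reduction should also bar up-titration is a separate choice for the sponsor.

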### 6.5.4. Criteria for Permanent Discontinuation of Study Drug

The occurrence of unacceptable toxicity not caused by the underlying disease will require that the study drug be permanently discontinued. Unacceptable toxicity is defined as follows:

- Occurrence of an AE that is related to study drug that, in the judgment of the investigator or the sponsor's medical monitor, compromises the participant's ability to continue study-specific procedures or is considered to not be in the participant's best interest.
- An AE requiring more than 2 dose reductions.
- Persistent AE requiring a delay of therapy for more than 2 weeks (14 days) unless a greater delay has been approved by the sponsor.
- Increase in QT/QTc to  $> 500$  milliseconds or to  $> 60$  milliseconds over baseline. In case of a QTc  $> 500$  milliseconds, the participant must be hospitalized and continuous ECG monitoring must be set up until the measure of the QTc interval decreases below 500 milliseconds and is acceptable in the opinion of the local cardiologist.

See Section 7 for discontinuation procedures.

## 6.6. Concomitant Medications and Procedures

All concomitant medications and treatments (including over-the-counter or prescription medicines, vitamins, vaccines, and/or herbal supplements) must be recorded in the eCRF. Any prior medication received up to 35 days before the first dose of study treatment and 30 to 35 days after the last dose of study treatment, or until the participant begins a new anticancer therapy, whichever occurs first, will be recorded in the eCRF. Any addition, deletion, or change in the dose of these medications will also be recorded. Concomitant medications administered after 30 to 35 days after the last dose of study treatment should be recorded for SAEs as defined in Section 9.2. Concomitant treatments/procedures that are required to manage a participant's medical condition during the study will also be recorded in the eCRF. The medical monitor should be contacted if there are any questions regarding concomitant or prior therapy.

### **6.6.1. Restricted Medications and Procedures**

Pemigatinib is predominantly metabolized by CYP3A4. There is an expected 50% increase in exposure in participants who concomitantly use CYP3A4 moderate inhibitors. However, as doses above the recommended Phase 2 dose of 13.5 mg QD have been tested (20 mg QD is tolerable), there is a sufficient safety margin. Therefore, the use of moderate CYP3A4 inhibitors is not prohibited but should involve careful monitoring, especially in relation to safety, while moderate CYP3A4 inducers and potent CYP3A4 inhibitors and inducers are prohibited (see [Appendix D](#)).

Careful monitoring is required when pemigatinib is concomitantly administered with OCT2 substrates such as dofetilide and metformin.

Calcium-based phosphate–binding medications should not be used due to a concern for soft tissue mineralization.

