### **2.2.2. Justification for Dose and Regimen**

Pemigatinib will be administered at 13.5 mg QD, continuously, for a cycle. Each cycle is 3 weeks. This dose and dosing schedule was selected based on emerging clinical and safety data from the INCB 54828-101 study, where the continuous dosing regimen was tested and has been tested in 12 and 14 participants at 9 mg and 13.5 mg QD continuous administration, respectively. In Study INCB 54828-101, the emerging safety data demonstrated that tolerability of the continuous dosing regimen of pemigatinib was comparable to that of intermittent dosing.

[figure not shown]
The hypothesis with a targeted therapy is that continued inhibition of the aberrant receptor may increase the potential for benefit from the treatment. Therefore, administering pemigatinib continuously will allow that consistent inhibition of the aberrant FGFR receptor in this population. Continuous dosing would still allow for dose holds for safety reasons with criteria and procedures for dose interruptions and adjustments clearly outlined in the Protocol.

Hyperphosphatemia is an expected on-target pharmacological effect of FGFR inhibition. The incidence of hyperphosphatemia, defined as any postbaseline phosphate level exceeding 5.5 mg/dL, has been observed in the majority of study participants treated with pemigatinib (refer to the [IB](#) for complete data). Some participants do not achieve hyperphosphatemia, and it is estimated that pharmacological concentration of pemigatinib in these participants is lower (see [Figure 2](#)). Therefore, up-titration of pemigatinib will be used to increase the exposure of pemigatinib in participants who do not achieve hyperphosphatemia when treated with 13.5 mg QD. The goal is to increase the serum concentration of pemigatinib.

The increase in serum phosphorus observed after treatment with pemigatinib was exposure-dependent and followed a sigmoid relationship. A population  $E_{max}$  model of pemigatinib AUC and maximal serum phosphate change from baseline was developed. For those participants treated with pemigatinib 13.5 mg who did not develop hyperphosphatemia,

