15. Active chronic or current infectious disease requiring systemic antibiotic, antifungal, or antiviral treatment within 2 weeks before enrollment (participants with asymptomatic chronic infections on prophylactic treatment are allowed).
16. Evidence of active HBV or HCV infection (defined as participants with elevated transaminases or cirrhosis. Participants with chronic HBV/HCV infection with no cirrhosis and no elevated transaminases are allowed).
17. Known HIV infection.
18. Current use of prohibited medication as described in Section [6.6.2](#).
19. Use of any potent CYP3A4 inhibitors or inducers or moderate CYP3A4 inducers within 14 days or five half-lives (whichever is longer) before the first dose of study drug/treatment. Note that moderate CYP3A4 inhibitors are not prohibited.
20. Known hypersensitivity or severe reaction to pemigatinib or excipients of pemigatinib (refer to the [IB](#)).
21. Inability or unlikelihood of the participant to comply with the dose schedule and study evaluations, in the opinion of the investigator.
22. Inadequate recovery from toxicity and/or complications from a major surgery before starting therapy.
23. Women who are pregnant or breastfeeding.
24. Any condition that would, in the investigator's judgment, interfere with full participation in the study, including administration of study drug/treatment and attending required study visits; pose a significant risk to the participant; or interfere with interpretation of study data.
25. Inability of the participant (or parent, guardian, or legally authorized representative) to comprehend the ICF or unwillingness to sign the ICF.
26. History of hypovitaminosis D requiring supraphysiologic doses (eg, 50,000 UI/weekly) to replenish the deficiency. Vitamin D supplements are allowed.

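### After up-titration to 18 mg, Section 6.5.1 allows a third dose reduction that Section 6.5.4 can forbid; a lesser point is that the CYP3A4 safety margin in 6.6.1 does not mention 18 mg

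*Protocol*

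**What the plan says.** **Up-titration.** All participants start at 13.5 mg once daily (Protocol 6.1). Under 6.5.3, a participant whose phosphate never exceeds 5.5 mg/dL in Cycle 1, who is compliant and who has no ongoing Grade 2 or higher related adverse event (AE) "will increase the daily dose to 18 mg starting from Cycle 2 Day 1". The participant must then agree to all Cycle 1 assessments at the new dose.

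**Dose reductions.**
- Section 6.5.1 recommends at most two reductions from 13.5 mg (to 9, then 4.5 mg). A separate paragraph gives up-titrated participants the sequence 13.5, 9, 4.5 mg. Nothing below 4.5 mg is allowed.
- Section 6.5.4 lists an AE that needs more than two reductions as unacceptable toxicity, for which permanent discontinuation is required. Section 7.1.1 repeats unacceptable toxicity under the reasons for which treatment must stop.
- Table 12 discontinues for recurrent Grade 3 toxicity after two reductions, with exceptions if the sponsor approves.
- Table 13 permanently discontinues if phosphate above 10 mg/dL recurs after two reductions.

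**Moderate CYP3A4 inhibitors.** Section 6.6.1 says "There is an expected 50% increase in exposure in participants who concomitantly use CYP3A4 moderate inhibitors". It takes 13.5 mg as the reference dose, notes that higher doses have been tested, and concludes "20 mg QD is tolerable), there is a sufficient safety margin". Moderate inhibitors are therefore allowed with careful monitoring. The section does not mention 18 mg.

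**The concern.** Up-titration is required for those who qualify, so every rule that depends on dose or on a count of reductions has to work from 18 mg as well as from 13.5 mg. The stopping rules count to two, which matches the ladder from 13.5 mg. The ladder from 18 mg has three steps.

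An investigator whose up-titrated participant needs a third reduction for the same AE finds one section that allows it and one that requires stopping. Two sites could treat the same case differently, each with the protocol behind it. SAP Section 8.2.3 counts participants who discontinue because of TEAEs, so that count would depend on which section the site followed.

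The 6.6.1 question is of the same kind but weaker: a rationale built around one dose is left to cover a higher one.

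**Working it through.** **1. Counting reductions**

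From 13.5 mg: 13.5 → 9 → 4.5 is 2 reductions. From 18 mg: 18 → 13.5 → 9 → 4.5 is 3 reductions. After two reductions the first participant is at 4.5 mg and the second at 9 mg.

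| Case | 6.5.1 | 6.5.4 | Agree? |
|---|---|---|---|
| Never up-titrated; one AE would need a third reduction | No step below 4.5 mg | Discontinue | Yes |
| Up-titrated; three reductions, no single AE needing more than two | 4.5 mg available | Not triggered | Yes |
| Up-titrated; one AE drives all three reductions | 4.5 mg available | Discontinue | **No** |

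Tables 12 and 13 use the same count of two and do not say whether a step from 18 to 13.5 mg is included. Neither says whether the two reductions must have been for the same toxicity.

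Stated exceptions differ. Table 12 allows one with sponsor approval, and so does the 6.5.4 bullet on treatment delay. The 6.5.4 bullet on reductions states none, nor does the Table 13 discontinuation entry.

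**2. The 6.6.1 margin**

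Inputs: 13.5 mg, a 50% increase and 20 mg (6.6.1); 18 mg (6.5.3). Formula: dose x (1 + increase), in mg-equivalents. This assumes dose-proportional exposure. Section 2.2.2 says "AUC for pemigatinib 18 mg was estimated using a linear exposure relationship"; carrying proportionality on to 27 mg-equivalents is this review's assumption.

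- At 13.5 mg: 13.5 x 1.5 = 20.25, and 20.25 / 20 = 1.01. This is level with the 20 mg that 6.6.1 cites. The protocol does not print the product; it is inferred from the section's own inputs.
- At 18 mg: 18 x 1.5 = 27.0, and 27.0 / 20 = 1.35.
- The 50% is approximate (2.2.2). For an assumed increase of 40% to 60%: 18 x 1.4 = 25.2 and 18 x 1.6 = 28.8.

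These are nominal figures. Of participants who do not become hyperphosphatemic at 13.5 mg, Section 2.2.2 says "it is estimated that pharmacological concentration of pemigatinib in these participants is lower". The readable text gives no size; Figure 2, titled "Comparison of Steady-State Exposures for Pemigatinib 13.5 mg QD Between Participants With Nonhyperphosphatemia and Hyperphosphatemia (C1D8", may show it, but its image is not available here. Assumed range:

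| Exposure lower by | 18 mg + moderate inhibitor |
|---|---|
| 10% | 27.0 x 0.90 = 24.3 |
| 20% | 27.0 x 0.80 = 21.6 |
| 25% | 27.0 x 0.75 = 20.25 (the 13.5 mg result) |
| 30% | 27.0 x 0.70 = 18.9 |

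**The case against.** **On the reduction rules.** Section 6.5.1 is permissive and 6.5.4 counts per AE, so they can be read together: three steps in all, but no more than two for any one AE. On that reading the third step still has a use, and a reader who inferred that the whole three-step ladder contradicts 6.5.4 would go too far. The reading narrows the conflict without settling it, because 6.5.1 does not limit the third step by AE and no section states the combined rule. One could also treat 18 to 13.5 mg as a return to the starting dose that does not count, but the current text does not say so. The Amendment 2 entry in Appendix F describes the ladder as three reductions. That is context, showing the ladder was deliberate, and is not itself an inconsistency.

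Section 6.5 places dose decisions in consultation with the medical monitor. This lowers the practical risk but does not say which section governs. The Table 13 overlap is probably rare, since up-titrated participants qualified by staying at or below 5.5 mg/dL in Cycle 1.

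**On 6.6.1.** Most of the objection stands. The section is silent on 18 mg; it sets no ceiling that 6.5.3 breaks. A reader might infer that 18 mg with a moderate inhibitor is unsafe. The documents do not support that: 20 mg is not called the highest tolerable dose, Section 2.3 reports no dose-limiting toxicities on monotherapy, and those who qualify for 18 mg are estimated to have lower exposure. Careful monitoring, repeat Cycle 1 assessments and phosphate testing after up-titration also apply. A participant already on an inhibitor in Cycle 1 is less likely to qualify. The repeat assessments do not by themselves cover an inhibitor started in a later cycle, which is the clearest gap.

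A reader might also compare 27.0 with 13.5 mg plus a prohibited potent inhibitor (13.5 x 1.88 = 25.4) and conclude that a permitted combination exceeds a banned one. That comparison is too fragile to use. It disappears if the moderate-inhibitor increase is 41% (18 x 1.41 = 25.4) or if exposure is 6% lower (27.0 x 0.94 = 25.4), and the ban is not stated as an exposure limit. Nor is exclusion criterion 19 at fault for lacking a dose limit: it governs entry, and everyone starts at 13.5 mg.

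**Conclusion.** The reduction rules are inconsistent as written, and this should be fixed. The conflict with 6.5.4 is confined to up-titrated participants in whom one AE drives all three reductions: at 9 mg, 6.5.1 leaves one more step open and 6.5.4 closes it. Tables 12 and 13 share the unexplained count of two. This conclusion rests on the text alone.

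The 6.6.1 point is a minor clarification. The stated margin corresponds to 13.5 mg (20.25 against 20) and was not extended to the 18 mg that 6.5.3 requires for eligible participants (nominally 27.0, or 25.2 to 28.8 for an assumed 40% to 60% increase). These figures depend on dose proportionality and average exposure, and fall if the up-titrated group has lower exposure. They show an incomplete rationale, not a hazard.

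How many participants either point would affect cannot be estimated from the documents. Power, alpha and endpoint definitions do not change.

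**What to change.** 1. Reconcile 6.5.1, 6.5.4, Table 12 and Table 13 so that one count of reductions applies after up-titration. State whether the step from 18 to 13.5 mg counts, whether the count is per AE or overall, and whether sponsor-approved exceptions apply to the 6.5.4 reductions bullet.
2. Reconcile 6.6.1 with 2.2.2 and 6.5.3. State whether the margin extends to 18 mg, including for an inhibitor started after up-titration, and on what exposure data. If the data behind Figure 2 support it, one sentence would do.

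Which clinical rule applies is left to the sponsor's clinical team. The cost is protocol wording in those sections and tables, plus a look at exposure data the sponsor already holds for item 2. Neither item needs new data collection from participants or a change to the SAP.
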